1.11 Pharmacokinetic

Pharmacokinetic (PK) concentrations will be summarized by epoch by means of arithmetic and geometric mean, median, standard deviation, minimum and maximum, coefficient of variation for arithmetic and geometric mean, the number of non-missing data points and the number of data points greater than zero. Sample number, date, scheduled timepoint, actual time of sample and days post dose (elapsed time) will also be listed.

1.12 Pharmacodynamics

Total IL-1 β

Total Interleukin-1 beta (IL-1 β) summary statistics (arithmetic and geometric mean, median, standard deviation, minimum and maximum, coefficient of variation for arithmetic and geometric mean, the number of non-missing data points and the number of data points greater than zero) will be displayed by epoch. Sample number, date, scheduled timepoint and actual time of sample will be listed.

1.12.1 Pharmacogenetics

Sample number, date, scheduled timepoint and actual time of sample will be listed.

1.13 Safety evaluation

All safety evaluations will be performed on the Safety set. For the overall analysis from baseline to epoch 4, patients who randomized to Placebo group at the beginning of epoch 2, only data after the first dose of ACZ885 will be included.

1.13.1 Adverse events

Adverse events will be coded using the MedDRA dictionary that provides the primary system organ class and preferred term information.

Adverse events will be summarized by presenting, for each cohort, epoch, initial randomized treatment and treatment sequence (as defined in [section 1.3](#)), the number and percentage of patients having any adverse event, having any adverse event in each primary system organ class and having each individual adverse event based on the preferred term. All other information collected (e.g. severity, relationship to study treatment) will be tabulated and listed as appropriate.

Adverse events will also be summarized by standardized MedDRA query (SMQ).

Exposure adjusted incidence rate of adverse events by primary system organ class and preferred term will be presented by epoch and according to the actual dose the patient receives.

Deaths, serious adverse events, and adverse events leading to discontinuation of study treatment will be summarized by primary system organ class and preferred term and listings will be provided.

Adverse events of special interest including identified and potential risks and adjudicated malignancy and infection events will be listed and summarized for each cohort, epoch and treatment group (as defined in [section 1.3](#)).

In addition, summary of adverse events and serious adverse events will be presented in combining the three cohorts. Adverse events occurring in follow-up period after discontinuation of study will be listed but not summarized in tables.

For the final analysis, AE/SAE will be reported using data after patients taking ACZ885 starting from epoch 2 to end of epoch 4.

For the legal requirements of ClinicalTrials.gov and EudraCT, two required tables on any ACZ group adverse events which are not serious adverse events with an incidence greater than 5% and on any ACZ group serious adverse events and SAE suspected to be related to study treatment will be provided by system organ class and preferred term on the safety set population.

If for a same patient, several consecutive AEs (irrespective of study treatment causality, seriousness and severity) occurred with the same SOC and PT:

- a single occurrence will be counted if there is ≤ 1 day gap between the end date of the preceding AE and the start date of the consecutive AE
- more than one occurrence will be counted if there is > 1 day gap between the end date of the preceding AE and the start date of the consecutive AE

For occurrence, the presence of at least one SAE / SAE suspected to be related to study treatment / non SAE has to be checked in a block e.g., among AE's in a ≤ 1 day gap block, if at least one SAE is occurring, then one occurrence is calculated for that SAE.

The number of deaths resulting from SAEs suspected to be related to study treatment and SAEs irrespective".

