3.1.2.2 Blinded escape (non-resolution/ early re-flare before Day 29)

The assignment to blinded escape will be managed by the IRT.

Patients whose index flare has not resolved by Day 15 will be eligible for blinded escape.

If patients experience persistent “mild”, “moderate” or “severe” disease activity (i.e., PGA ≥ 2 [clinical flare]), or CRP persistent >10 mg/L with less than 40% reduction from baseline from Day 8 to Day 14, they will also be eligible for blinded escape at an unscheduled visit.

In case one of the conditions described above occurs, patients will receive a single add-on s.c. injection of canakinumab (150 mg s.c. [or 2 mg/kg for patients ≤ 40 kg]) from Day 8 to Day 28 but will not be unblinded to their randomized treatment (see [Table 3-1](#)). This will lead to blinded up-titration to the next dosing regimen according to the initial randomized treatment and will be initiated from Day 29 onward through IRT.

- Patients randomized to canakinumab 150 mg q4w will receive 2 injections of canakinumab on Days 29, 57 and 85 equaling to a canakinumab 300 mg q4w regimen
- Patients randomized to placebo will receive 1 injection of canakinumab and 1 injection of placebo each on Days 29, 57 and 85 equaling to a canakinumab 150 mg q4w regimen

If the patient’s condition is not improving after add-on injection, rescue medication should be used from Day 15 until treatment is administered at Day 29. All patients on blinded escape will be followed-up for efficacy and safety.

Non-randomized cohort

Canakinumab naïve Japanese crFMF patients with non-exon 10 mutations or patients >28 days but <2 years old will initiate open-label treatment receiving canakinumab 150 mg (or 2 mg/kg for patients weighing ≤ 40 kg) q4w at Day 1. Index flare resolution will be assessed at Day 15.

Patients experiencing persistent “mild”, “moderate” or “severe” disease activity (i.e., PGA ≥ 2 [clinical flare]), or CRP persistent >10 mg/L with less than 40% reduction from baseline from Day 8 to Day 28 can receive a single add-on s.c. injection of canakinumab (150 mg s.c. [or 2 mg/kg for patients ≤ 40 kg]). If the patient’s condition is not improving after add-on injection, rescue medication should be used until the patient’s next visit at Day 29 when study treatment will be administered.

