1.2 Subjects and treatments

The following analysis sets will be used for the data analysis.

The **Randomized Set** Epoch 2 will consist of all patients who are randomized in the randomized treatment epoch (Epoch 2).

The **Randomized Set** Epoch 3 will consist of all patients who received canakinumab drug in epoch 2 and are responders at week 16 and who are re-randomized in the randomized withdrawal epoch (Epoch 3).

Unless otherwise specified, mis-randomized patients (mis-randomized in IRT) will be excluded from the randomized set. (Mis-randomized patients are defined as cases where IRT contacts were made by the site either prematurely or inappropriately prior to confirmation of the patient's final randomization eligibility and no study medication was administered to the patient).

The **Full Analysis Set (FAS)** Epoch 2 will consist of all randomized patients in the randomized treatment epoch who received at least one dose of study drug in epoch 2. Following the intent-to-treat principle, patients will be analyzed according to the treatment they were assigned to at randomization.

The **Full Analysis Set (FAS)** Epoch 3 will consist of all patients in the randomized withdrawal epoch who received at least one dose of study drug.

The **Safety Set** Epoch 2 will consist of all patients that received study treatment in Epoch 2. Patients will be analyzed according to treatment received. Of note, the statement that a subject had no AEs also constitutes a safety assessment.

The **Safety Set** Epoch 3 will consist of all patients that received study treatment in Epoch 3. Patients will be analyzed according to treatment received. Of note, the statement that a subject had no AEs also constitutes a safety assessment.

The **Safety Set** Epoch 4 will consist of all patients that received study treatment in Epoch 4. Patients will be analyzed according to treatment received. Of note, the statement that a subject had no AEs also constitutes a safety assessment.

The **Per-protocol Set (PPS)** Epoch 2 will consist of all patients in the FAS Epoch 2 who do not fulfill any criteria that could potentially confound the interpretation of analyses conducted on the FAS.

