1.4 Summary of the analyses

Table 1-2 Analysis by Epoch

Endpoint/analysis	Epoch			
	Epoch 2 (restricted to initial randomized treatment arms)	Epoch 2	Epoch 3	Epoch 4
Patient disposition	X	X	X	X
Demography & baseline characteristics	X	X	X	X
Medical history	X			
Previous & concomitant medication	X	X	X	X
Surgeries and medical procedures		X	X	X
Rescue medications	X	X	X	X
Study medication: duration of exposure	X	X	X	X
Proportion of responders at week 16	X			
Supportive analysis using SAA	X			
patients who achieve a PGA < 2 at Week 16	X			
Serologic remission at week 16	X			
Normalized SAA	X			
Responder in epoch 3 (only for canakinumab responder in epoch 2)			X	
CRP		X	X	X
PGA		X	X	X
PPGA		X	X	X
Physician's severity assessment of disease signs and symptoms over time		X	X	X
Fever		X	X	X
Blinded escape	X			
Time to new flare			X	
AIDAI	X	X	X	
SF-12	X	X	X	
CHQ-PF50	X	X	X	
SDS v3	X	X	X	
Total IL-1 β		X	X	X
Adverse events		X	X	X
Laboratory data		X	X	X
Vital signs		X	X	X
ECG		X	X	X

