1.13.2 Local injection site tolerability

Local injection site tolerability will be assessed on the injection site (separately from the adverse event page). Each patient will be classified into one of the following four categories (based on AE ATC grade):

1. No tolerability reactions at any time in the trial.
2. A mild reaction (grade 1) observed on at least one occasion but no moderate or severe/ potentially life threatening reactions.
3. A moderate reaction (grade 2) observed on at least one occasion but no severe/ potentially life threatening reactions.
4. A severe (grade 3) or potentially life threatening (grade 4) reaction observed on at least one occasion.

The number and percentage of patients in each category will be presented for each cohort, epoch, initial randomized treatment and treatment sequence (as defined in [section 1.3](#)). In addition, summary of pre-specified symptoms (Erythema/Redness, Tenderness, Induration/Swelling, Pain) will be provided. All details of injection site reactions will be listed.

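### Epoch 2 AE and injection-site counts by randomized arm have no cut at escape, so placebo columns can hold events on canakinumab; the planned actual-dose rates correct this only for AEs by SOC and PT

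*SAP*

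**What the plan says.** **Grouping.** SAP 1.13.1: "Adverse events will be summarized by presenting, for each cohort, epoch, initial randomized treatment and treatment sequence". SAP 1.13.2, for injection-site reactions: "The number and percentage of patients in each category will be presented for each cohort, epoch, initial randomized treatment and treatment sequence". Neither section states an at-risk period within Epoch 2. The lowest injection-site category is worded "No tolerability reactions at any time in the trial", which is not tied to the randomized drug.

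**Escape.** Under Protocol 3.1.2.2, patients in either arm who meet the escape criteria between Day 8 and Day 28 are handled as follows: "patients will receive a single add-on s.c. injection of canakinumab". From Day 29 the placebo patients among them stay on canakinumab and the canakinumab patients go to the higher dose. Protocol 3.1.2.3 adds open-label escape from Day 29.

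**Where a cut is written.** SAP 1.13 gives one, but only where safety data are summarized across all treatment epochs together: "patients who randomized to Placebo group at the beginning of epoch 2, only data after the first dose of ACZ885 will be included". Section 1.13.1 repeats the idea for the final analysis. Neither covers the Epoch 2 tables.

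**What already helps.** SAP 1.13.1 plans exposure-adjusted AE rates by SOC and PT that "will be presented by epoch and according to the actual dose the patient receives".

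**Other relevant text.** The Safety Set rule in SAP 1.2 is "Patients will be analyzed according to treatment received". Table 1-2 has a column headed "Epoch 2 (restricted to initial randomized treatment arms"), and adverse events are not marked in it.

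**The concern.** Epoch 2 is the only placebo-controlled comparison that starts free of canakinumab. If an escaped placebo patient is counted in the placebo column for the whole epoch, reactions to canakinumab in that patient are reported as placebo events. A true excess would then look smaller in the tables a reader consults first.

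The treatment-sequence display in SAP 1.3 does not repair this. The switched columns (placebo to 150 mg, and onward to 300 mg) hold events from before and after the switch. The unswitched columns keep only patients with no flare, add-on or up-titration, so they are selected on outcome after randomization. Neither display sets time on placebo against time on canakinumab.

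**Working it through.** The documents give no AE rate and no escape rate, so there is no stated figure to reproduce. What follows is a scenario calculation. Escape shares, escape days and event rates are assumptions; the 112 days and the visit days come from the Protocol.

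**1. Time on canakinumab after escape.** For a placebo patient escaping on day d, the share of Epoch 2 is (113 − d)/112:
- Day 8: 105/112 = 94%
- Day 15: 98/112 = 87.5%
- Day 29: 84/112 = 75%
- Day 57: 56/112 = 50%
- Day 85: 28/112 = 25%

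**2. Apparent rate ratio.** If a share e of the placebo arm escapes on day d, then f = e × (113 − d)/112 of placebo-arm time is on canakinumab. With constant rates and true ratio R, the by-arm ratio is R/(1 − f + fR). For escape at Day 29:

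| e | f | R = 0.5 | R = 1 | R = 1.5 | R = 2 | R = 3 |
|---|---|---|---|---|---|---|
| 20% | 0.150 | 0.54 | 1.00 | 1.40 | 1.74 | 2.31 |
| 50% | 0.375 | 0.62 | 1.00 | 1.26 | 1.45 | 1.71 |
| 70% | 0.525 | 0.68 | 1.00 | 1.19 | 1.31 | 1.46 |
| 90% | 0.675 | 0.75 | 1.00 | 1.12 | 1.19 | 1.28 |

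For R = 2 with escape between Day 15 and Day 57, the range is 1.82 (20%, Day 57) to 1.12 (90%, Day 15). With no true effect there is no distortion.

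**3. Patient percentages.** The by-arm tables report patients with an event, not rates. Assume 20% incidence on placebo over 112 days and R = 2. Incidence on canakinumab is 1 − 0.8² = 36.0%, a difference of 16.0 points. With share e escaping at Day 29, placebo-arm incidence is 1 − [(1 − e) × 0.8 + e × 0.8^(0.25 + 2 × 0.75)]. For e = 20%, 50%, 70% and 90% this gives 22.5%, 26.2%, 28.6% and 31.1%, so differences of 13.5, 9.8, 7.4 and 4.9 points.

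**4. Dose rise in the canakinumab arm.** If a share c of that arm moves to 300 mg at Day 29, g = 0.75c and the ratio is [R150(1 − g) + R300 × g]/(1 − f + f × R150). Take R150 = 2 and an assumed R300 = 3:
- e = 70%, c = 20%: (1.70 + 0.45)/1.525 = 1.41
- e = 20%, c = 60%: (1.10 + 1.35)/1.15 = 2.13, above the true 150 mg ratio

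The second case needs canakinumab patients to escape three times as often as placebo patients.

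**5. Injection-site reactions.** These follow injections, so a constant rate per day is only a rough guide. Counting occasions instead, a placebo patient with an add-on at Day 15 is injected on Days 1, 15, 29, 57 and 85, and four of those five occasions include canakinumab. With open-label escape at Day 29 it is three of four.

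**6. Is substantial placebo escape plausible?** Entry requires more than 6 flares a year (recurrent TRAPS), at least 3 in 6 months (HIDS) or at least 1 attack a month (crFMF). Over 112 days that is about 6 × 112/365 = 1.8 to 12 × 112/365 = 3.7 attacks. This makes escape plausible but gives no escape rate, because not every attack meets the PGA and CRP criteria.

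**The case against.** **Actual-dose rates are planned.** They place an escaped placebo patient's later events and time under canakinumab, and infections are a SOC. Protocol 9.5.3.1 also calls for adjustment for treatment-group exposure. This stands. A reader might infer that every Epoch 2 harm comparison is pulled toward no difference; the documents do not support that for AEs by SOC and PT. These rates pool patients across arms by dose, however, so they are not a randomized comparison.

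**It is unclear whether a by-arm AE table exists.** Table 1-2 does not mark one, SAP 1.3 shows Epoch 2 safety data in sequence columns, and Protocol 9 lists placebo and placebo-to-canakinumab as separate arms. The phrase in 1.13.1 could mean arm crossed with sequence. The ambiguity is real and is part of the point. SAP 1.5 does use the two groupings as separate displays, and injection-site reactions have no row in Table 1-2. If only sequence columns are produced, their own defects remain. The treatment-received rule does not say how to count a patient who received both.

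**SAEs, deaths and discontinuations.** A reader might infer that these are diluted in by-arm tables, along with adjudicated infections. SAP 1.13.1 states no grouping for the first three, and puts events of special interest in the section 1.3 groups. What can be said is that no actual-dose rates are stated for SAEs or AEs leading to discontinuation.

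**Direction and size are not fixed.** Correct: step 4 shows an offset, and all shares are assumed.

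**A cut brings its own bias.** Escape depends on PGA and CRP, so stopping there is informative, and placebo follow-up may be as short as a week. This stands and limits the remedy.

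**The limit is disclosed.** Protocol 3.2 concedes that escape may leave limited placebo-controlled safety data. That is a reason to attribute the available data clearly.

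**Conclusion.** Followed as written, the by-arm Epoch 2 counts of AEs and injection-site reactions include events that escaped placebo patients have on canakinumab. The absence of a cut is read from silence, but an unstated at-risk period is itself the defect.

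Where placebo patients escape more often than canakinumab patients, a true excess would be expected to shrink. At assumed escape shares of 20% to 90% at Day 29, a true ratio of 2 becomes 1.74 to 1.19, and a 16.0-point difference becomes 13.5 to 4.9 points. This rests on constant rates, escape unrelated to event risk and no dose effect in the canakinumab arm. Shrinkage is the expected direction, not a certain one.

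The actual-dose rates correct the misattribution for AEs by SOC and PT. The gap remains for SAEs, AEs leading to discontinuation and, most clearly, injection-site reactions, which have by-arm and sequence counts but no actual-dose display.

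**What to change.** 1. Keep the by-arm tables in SAP 1.13.1 and 1.13.2 and state their at-risk period. Add an Epoch 2 version by initial randomized treatment that counts only events with onset before the first canakinumab dose (placebo arm) or before the first add-on or up-titration (canakinumab arm). Give person-time and exposure-adjusted rates beside the counts, because the arms stop at different times. Show post-escape events in separate columns.
2. Extend the actual-dose exposure-adjusted rates to SAEs, AEs leading to discontinuation and injection-site reactions.
3. Reconcile 1.13.1 with Table 1-2, so that it is clear whether AEs are tabulated by initial randomized arm.

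**Cost.** SAP text and programming only. Protocol 5.5.4 already requires all dose changes to be recorded, and Protocol 8.3 has them tracked in the IRT. The pre-escape period is short and will hold few events. The cut version should carry a note that escape depends on disease activity, so that it is read beside the uncut tables.

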³ Only applicable for pediatric patients

⁴ The AIDAI and PPGA will be completed by the patient on an electronically diary daily from Screening till TD or PSW

⁵ Applicable for patients whose index flare has not resolved by Day 15. Blinded-escape add-on treatment may be initiated from Day 8 to Day 28

⁶ Applicable for patients on randomized treatment who flare on/ after Day 29 or patients on blinded-escape who will still have “mild”, “moderate” or “severe” disease activity (PGA ≥ 2 [clinical flare] and CRP ≥ 30 mg/L [serological flare]) or re-flare

Table 6-2 **Assessment schedule:**
Randomized withdrawal epoch (Epoch 3) and open-label treatment epoch (Epoch 4)

TD = Investigational treatment discontinuation

PSW = Premature subject withdrawal

X = assessment to be recorded on clinical data base

S = assessment to be recorded on source documentation

*These assessments are also to be conducted for patients who discontinue

#These assessments are source documentation only and will not be entered into the CRF

¹ To be performed 30 days following TD or PSW, or 8 weeks after last injection of investigational drug, whichever is later

² Only applicable for TRAPS patients rolling-over from CACZ885D2203/ CACZ885D2207M i.e. patients directly entering Epoch 3 following screening

³ Only applicable for pediatric patients

⁴ The AIDAI and PPGA will be completed by the patient on an electronically diary daily till Day 281 or PSW

⁵ Patients up-titrated to q4w administration in Epoch 4, will come back every 4 weeks for unscheduled visits at Day 309, Day 365, Day 421, Day 477, Day 533, Day 589, Day 645, Day 701 and Day 757 in addition to the scheduled visits

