7.2 Serious adverse events

7.2.1 Definition of SAE

An SAE is defined as any AE (appearance of (or worsening of any pre-existing) undesirable sign(s), symptom(s) or medical conditions(s) which meets any one of the following criteria:

- is fatal or life-threatening
- results in persistent or significant disability/incapacity
- constitutes a congenital anomaly/birth defect
- requires inpatient hospitalization or prolongation of existing hospitalization, unless hospitalization is for:
 - a. routine treatment or monitoring of the studied indication, not associated with any deterioration in condition (specify what this includes)

- b. elective or pre-planned treatment for a pre-existing condition that is unrelated to the indication under study and has not worsened since signing the informed consent form
- c. treatment on an emergency outpatient basis for an event not fulfilling any of the definitions of a SAE given above and not resulting in hospital admission
- d. social reasons and respite care in the absence of any deterioration in the patient's general condition

- is medically significant, i.e. defined as an event that jeopardizes the patient or may require medical or surgical intervention.

Life-threatening in the context of a SAE refers to a reaction in which the patient was at risk of death at the time of the reaction; it does not refer to a reaction that hypothetically might have caused death if more severe (see Annex IV, ICH-E2D Guideline).

All malignant neoplasms will be assessed as serious under “medically significant” if other seriousness criteria are not met.

Any suspected transmission via a medicinal product of an infectious agent is also considered a serious adverse reaction.

Medical and scientific judgment should be exercised in deciding whether other situations should be considered serious reactions, such as important medical events that might not be immediately life threatening or result in death or hospitalization but might jeopardize the patient or might require intervention to prevent one of the other outcomes listed above. Examples of such events are intensive treatment in an emergency room or at home for allergic bronchospasm, blood dyscrasias or convulsions that do not result in hospitalization.

If all AEs (serious and non-serious) are captured on the CRF, SAEs are monitored continuously and have also special reporting requirements; see [Section 7.2.2](#).

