7.2.2 SAE reporting

To ensure patient safety, every SAE, regardless of causality, occurring after the patient has provided informed consent and until 30 days following TD or PSW, or 8 weeks after last injection of study drug, whichever is later must be reported to Novartis within 24 hours of learning of its occurrence.

Any SAEs experienced after this period should only be reported to Novartis if the investigator suspects a causal relationship to study treatment.

Recurrent episodes, complications, or progression of the initial SAE must be reported as follow-up to the original episode, regardless of when the event occurs. This report must be submitted within 24 hours of the investigator receiving the follow-up information. An SAE that is considered completely unrelated to a previously reported one should be reported separately as a new event.

Information about all SAEs (either initial or follow up information) is collected and recorded in English on the paper Serious Adverse Event Report Form or the electronic Serious Adverse Event Form within the Oracle Clinical/Remote Data Capture (OC/RDC) system (where

available). The Investigator must assess the relationship to each specific component of the study treatment (if the study treatment consists of several components).

SAEs (initial and follow-up) that are recorded *on the paper SAE form* should be faxed within 24 hours of awareness of the SAE to the local Novartis Drug Safety and Epidemiology Department. The telephone and fax number of the contact persons in the local department of Drug Safety and Epidemiology, specific to the site, are listed in the investigator folder provided to each site. The original copy of the SAE Report Form and the fax confirmation sheet must be kept with the case report form documentation at the study site. Follow-up information should be provided using a new paper SAE Report Form stating that this is a follow-up to a previously reported SAE

SAEs (initial and follow-up) that are recorded *electronically* in the OC/RDC system should be entered, saved and e-signed within 24 hours of awareness of the SAE or changes to an existing SAE. These data will automatically be submitted to Novartis Drug Safety & Epidemiology immediately after investigator signature or 24 hours after entry, whichever occurs first.

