9.5.3.1 Adverse events

Adverse events will be coded using the MedDRA dictionary that provides the primary system organ class and preferred term information.

Adverse events will be summarized by presenting, for each cohort, epoch and treatment group, the number and percentage of patients having any adverse event, having any adverse event in each primary system organ class and having each individual adverse event based on the preferred term. Exposure adjusted incidence rate of AEs will also be provided. All other information collected (e.g. severity, relationship to study treatment) will be tabulated and listed as appropriate.

Adverse events will also be summarized by SMQ. Adverse event analyses will be adjusted for treatment group exposure in each epoch.

Deaths, serious adverse events, and adverse events leading to discontinuation of study treatment will be summarized by primary system organ class and preferred term and listings will be provided.

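### SAP 1.13.1 lists but does not tabulate adverse events after study exit, with no exception for SAEs or deaths, which conflicts with the same section and with the protocol

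*SAP*

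**What the plan says.** Four statements bear on this point.

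- SAP 1.13.1, on events after study exit: "Adverse events occurring in follow-up period after discontinuation of study will be listed but not summarized in tables".
- SAP 1.13.1, a few lines earlier, with no cut-off date: "Deaths, serious adverse events, and adverse events leading to discontinuation of study treatment will be summarized by primary system organ class and preferred term". For the final analysis the section adds that "AE/SAE will be reported using data after patients taking ACZ885 starting from epoch 2 to end of epoch 4", and names no follow-up period.
- Protocol 7.2.2 requires every SAE, whatever its cause, to be reported "until 30 days following TD or PSW, or 8 weeks after last injection of study drug, whichever is later". TD is discontinuation of investigational treatment and PSW is premature subject withdrawal. Footnote 1 to Protocol Table 6-2 times the follow-up contact by the same rule: "To be performed 30 days following TD or PSW, or 8 weeks after last injection of investigational drug, whichever is later".
- Protocol 9.5.3.1 says "Deaths, serious adverse events, and adverse events leading to discontinuation of study treatment will be summarized by primary system organ class", and contains no rule that moves follow-up events to a listing.

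The SAP sentence on AEs covers SAEs because, in Protocol 7.2.1, "An SAE is defined as any AE" that meets a seriousness criterion. SAP 1.9 applies a parallel listing-only rule to concomitant medication, so the AE sentence looks like a general convention and not a slip.

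**The concern.** The protocol obliges sites to report SAEs for a defined period after a patient leaves, and it promises a summary of SAEs and deaths. The SAP then takes that same period out of the tables and gives no reason. A programmer cannot follow both SAP sentences for a death that occurs after study exit. One says to summarize it and the other says to list it only. The SAE and death tables for the public registries, specified at the end of SAP 1.13.1, carry the same ambiguity because they have no follow-up cut-off either.

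At stake are the crude percentages of patients with an SAE, a fatal event or a serious event of special interest. Their denominators are numbers of patients, so leaving out post-exit events can only lower these percentages or leave them unchanged. With small arms, one patient is visible in the result.

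**Working it through.** The plan gives no figure of its own to reproduce, and the documents contain no event counts. The check is date arithmetic on the reporting window.

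**Inputs**
- Reporting window: the later of 30 days after TD/PSW and 8 weeks (56 days) after the last injection (Protocol 7.2.2; Table 6-2, footnote 1).
- Tabulation stops at discontinuation of study (SAP 1.13.1).
- Planned arm size in Epoch 2: 30 per arm in each cohort (Protocol section 4).
- Assumption: the 30-day limb is counted from study exit. The protocol does not say which date governs when TD comes well before PSW.

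**Formulas.** Let t be the days from last injection to study exit.
- The window ends max(t + 30, 56) days after the last injection.
- Untabulated part of the window = max(t + 30, 56) − t = max(30, 56 − t) days.
- Untabulated share of the 8 weeks after the last injection = max(0, 56 − t)/56.

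| t (days) | Window ends (days after last injection) | Untabulated days | Share of the 8 weeks untabulated |
|---|---|---|---|
| 0 | 56 | 56 | 100% |
| 7 | 56 | 49 | 87.5% |
| 14 | 56 | 42 | 75% |
| 26 | 56 | 30 | 53.6% |
| 28 | 58 | 30 | 50% |
| 42 | 72 | 30 | 25% |
| 56 | 86 | 30 | 0% |

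Eight weeks after the last injection is therefore the minimum length of the window. The window is longer for anyone who leaves more than 26 days after the last injection.

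**Share of all collected time that is untabulated, for assumed exit days**
- Dosed and leaving on Day 29: 56/(28 + 56) = 66.7%.
- Last injection Day 85, leaving Day 113: 30/(112 + 30) = 21.1%.
- Leaving Day 785, last injection Day 729 or Day 757: 30/(784 + 30) = 3.7%. This case counts only if the rule covers completers, which the SAP does not state.

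**Effect on a percentage.** In an Epoch 2 table by initial randomized arm, one additional patient with an SAE moves the result by 1/30 = 3.3 points, provided that patient is not already counted. This figure does not carry over to Epoch 3. There only canakinumab patients who needed no escape are re-randomized (Protocol 3.1.3.1), and the display is by no up-titration or by cumulative dose (SAP 1.3).

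**Exposure-adjusted rates.** SAP 1.13.1 does not name the denominator. If it is the exposure of SAP 1.8, that also ends at the last visit in the epoch, so follow-up is missing from numerator and denominator alike. The rate is then too low if events are more frequent after exit than before, and too high if they are less frequent. The documents do not say which.

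**The case against.** The best defence is that the SAP already says deaths and SAEs will be summarized, so the listing-only sentence may be meant for ordinary AEs. That is a possible reading, and it makes part of the problem an unreconciled pair of sentences. It does not settle the matter, because neither sentence refers to the other and no exemption is written.

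The second defence is that the trigger is leaving the study, not stopping treatment. This stands. Protocol 5.5.9 keeps patients who stop treatment in the study, and Protocol 6.5 makes safety assessments mandatory for those who must stop permanently. Their events are tabulated until they exit. Where consent is withdrawn, Protocol 5.5.10 ends assessments and restricts contact, so few follow-up data would exist.

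A reader might infer that the rule selectively removes patients who left because of an adverse event. The documents do not support that. They give no reasons for exit, the design keeps patients who stop for an event under observation, and the SAP does not say whether completers are also covered. A reader might also infer that the events disappear from the report. They remain in the listings.

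A third objection concerns the remedy. The scheduled follow-up in Protocol section 6 is a visit or phone call for SAEs, so non-serious AEs are not systematically sought. Tabulating every AE and adding the follow-up time to every denominator would dilute non-serious AE rates. That is right, and the remedy must be limited to serious events.

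**Conclusion.** The point holds as a conflict within SAP 1.13.1, and between it and Protocol 7.2.2 and 9.5.3.1. Applied literally, the SAP keeps SAEs and deaths after study exit out of the summary percentages, although the protocol makes the SAEs reportable and promises the summary. The untabulated stretch is 30 to 56 days per patient leaving, depending on how recently the patient was dosed, if the 30-day limb runs from study exit.

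Two stronger conclusions are not supported. The size of any change in the safety results cannot be stated, because it depends on events the documents do not report; 3.3 points per newly counted patient is an Epoch 2 illustration only. Downward bias in the exposure-adjusted rates is not shown, because exposure as defined in SAP 1.8 stops at the same visit. The change should be made because it is specific and cheap and uses data the protocol already requires.

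**What to change.** Replace the listing-only sentence in SAP 1.13.1 with rules to this effect:

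1. Listing-only treatment after study exit applies to non-serious AEs and to events with onset after the SAE reporting window of Protocol 7.2.2.
2. SAEs, and events of special interest that are SAEs, with onset within that window are tabulated under the last treatment received, either in the main tables or in a dedicated follow-up table.
3. All reported deaths are tabulated, whenever they occur.
4. Where exposure-adjusted SAE rates are given, the matching follow-up time is added to the SAE denominator only. Denominators for non-serious AEs stay as they are.
5. The text states whether discontinuation of study includes patients who complete.

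The cost is SAP wording and minor programming. No new data are needed, because the SAE reports are already mandatory. The downside for the sponsor is that SAE and death percentages may look slightly less favourable.
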